5.4 LIFESTYLE CONSIDERATIONS

During the SARA-INT 6-month treatment phase, all participants are asked to avoid a sedentary lifestyle and to try to perform at least 30 minutes of physical activity per day, at least 5 days per week. Physical activities can consist of walking, going for groceries, gardening, housekeeping, and light exercise (at home or outdoors) but only if the participant is already used to performing them on a routine basis.

Of note, walking and other physical exercise will be automatically recorded via a wearable actimetry device for later analyses. With this aim, all participants will be requested to wear the actimetry device most of the time as a wrist watch, including at night. They are expected to remove it only during showers and/or baths.

A structured physical exercise program should not be started during the study treatment phase.

During this study, participants are also asked to maintain a healthy diet and to avoid excessive or low food intake. A brochure reminding participants of simple rules for a healthy, nutritional diet will be provided to all participants.

5.5 SCREEN FAILURES

Screen failures are defined as participants who consent to participate in the clinical trial but are not subsequently randomized into the study. A minimal set of screen failure information is required to ensure transparent reporting of screen failure participants, to meet the Consolidated Standards of Reporting Trials (CONSORT) publishing requirements and to respond to queries from regulatory authorities. Minimal information includes demography, screen failure details, eligibility criteria, and any SAEs.

Individuals who do not meet the criteria for participation in this trial (screen failures) because of a temporary exclusion criterion may be re-screened after 3 months. These re-screened participants should be assigned the same participant number from the initial screening. Investigational sites are allowed to rescreen a participant who had borderline results for an eligibility criterium (*i.e.* SPPB=9) 6 to 12 months after their first screening, if the subject complains from a decline in his.hr physical abilities. These rescreened participants should be assigned with a new participant number compared to the first screening. Participants can only be screened twice.

5.6 STRATEGIES FOR RECRUITMENT AND RETENTION

Mass mailings, posters or videos in the hospital/clinic waiting rooms, presentation of the SARA-INT study in local newspapers, on TV, radio broadcasting or on social media by the PI and

Investigators are all strategies that will be considered, made available and implemented/adapted according to the local policies and regulations. In addition, app-based tools could also be utilized.

A dedicated website to present the study to the general public is available online (https://mysara.eu/#/) and could be referenced by institutional websites.

Transportation vouchers could be provided to participants according to local policies and legislation.

6 STUDY INTERVENTION

6.1 STUDY INTERVENTION(S) ADMINISTRATION

6.1.1 STUDY INTERVENTION DESCRIPTION

The investigational product BIO101 is prepared in accordance with Good Manufacturing Practice (GMP) as required by Good Clinical Practice (GCP).

The BIO101 active principle ingredient is 20E,

Placebo was prepared in accordance with GMP as required by the current GCP

A Certificate of Analysis (CoA) is included in the CMC IMPD (Chemistry, Manufacturing and Controls Investigational Medicinal Product Dossier).

6.1.2 DOSING AND ADMINISTRATION

Three doses are tested in this study: 175 mg b.i.d. of BIO101, 350 mg b.i.d. of BIO101 or placebo b.i.d. A rationale for the doses selected of the study drug is provided in section 4.3.

Administered daily dose is the same throughout the whole treatment period.

All therapeutic units (175 mg BIO101 b.i.d. or 350 mg BIO101 b.i.d. or placebo b.i.d.) are identical in compliance with the double-blind process.

Study participants are instructed by the investigator or the investigation center staff to start the treatment the day after randomization; e. g. if the participant is randomized on Friday, he/she will start the investigational treatment on Saturday morning.

Each administration is made of two capsules, to be taken by oral route, swallowed with water or fruit juice or other common soft drinks. Capsules should be taken twice a day: once in the morning and once in the evening. Those can be taken with a meal such as breakfast or dinner,

approximately 12 hours apart. If the participant forgets or is not able to take the capsules at the appointed time, he/she should be instructed not to make up for the missed pills; i.e. to not take more capsules later in the day or the day after.

The four capsules to be taken daily is the same across the entire 6-month treatment period.

Important note: Date of each next visit should be calculated back on Day 0 visit (baseline) in order to not exceed the total duration of 26 weeks of treatment.

6.2 PREPARATION/HANDLING/STORAGE/ACCOUNTABILITY

6.2.1 ACQUISITION AND ACCOUNTABILITY

management of TU packages and TU delivery to EU investigation centers. The order to deliver the initial stock and further reorders of individual investigation centers will be

given by the contract research organization, according to the center's actual enrollment rate.

Return of expired TUs or unused TUs will be ordered by Biophytis. Detailed information on TU handling will be provided in a Manual of Procedures (MOP).

6.2.2 FORMULATION, APPEARANCE, PACKAGING, AND LABELING

 BIO101 is formulated as a capsule that includes 175 mg of the active principle ingredient,

 20E,

 Placebo is manufactured as an identical size 1 opaque capsule containing

Capsules containing BIO101 and placebo are opaque and identical in appearance. The matching placebo capsule Stability was tested following ICH regulations. In order to be fully compliant, the drug substance and the excipients are controlled according to the FDA and European pharmacopeia.

The study drug is packaged in

The study drug was labelled according to local law and regulatory requirements. All TUs had to be stored as specified at delivery and in the original packaging. In case of a deviation in storage conditions, the clinical site cannot dispense the affected study drug and have to notify Biophytis right away. Utmost care will be taken to correctly dispense the study drugs as assigned by the randomization system embedded within the eCRF.

TUs are made up of	Tł	ne	is called a	kit. Each	kit is ind	ividually
numbered.			-			
Fach have				1.1.4		

The actual capsule combinations correspond to daily doses of 175 mg b.i.d., 350 mg b.i.d. or placebo.

The box is conceived to be elderly friendly (US and EU), and child proof (for US only). Each individual study participant will receive a total of **Sector** over the 6-month period, released to the study participant according to the timeline of the study: **Sector** at randomization /baseline visit; **at the Month 1 visit**, and **Sector** at the Month 3 visit.

Detailed information on TU dispensing will be provided in a MOP.

A representative labeling of the drug product is presented below:

Clinical Study Number: BIO101-CL03 Study treatment: "BIO101, or placebo" Batch Number: # capsules of BIO101 (175mg capsule) or placebo, per box Oral route, 4 capsules per day (two on the morning and two on the evening) To be swallowed entirely without opening the capsules Expiration Date: #

Kit Number: #

Patient ID (to be completed at the center before supplying the patient)
Investigator Name (to be completed at the center before supplying the patient)
Visit Number (to be completed at the center before supplying the patient)
Date dispensed (to be completed at the center before supplying the patient)

Store at away from light and humidity CAUTION: New Drug--Limited by Federal (or United States) law to investigational use Drug for investigational use – keep out of the reach of children Please return non-used capsules and empty boxes to your center at the end of the study

Sponsor: Biophytis, [name] telephone:

6.2.3 PRODUCT STORAGE AND STABILITY

Based on the available stability data of the Drug Product, Biophytis currently certifies a shelf life of the stability data of the Drug Product, Biophytis currently certifies a shelf life of the stability data of the Drug Product, Biophytis currently certifies a shelf life of the stability data of the Drug Product, Biophytis currently certifies a shelf life of the stability data of the Drug Product, Biophytis currently certifies a shelf life of the stability data of the Drug Product, Biophytis currently certifies a shelf life of the stability data of the Drug Product, Biophytis currently certifies a shelf life of the stability data of the Drug Product, Biophytis currently certifies a shelf life of the stability data of the Drug Product, Biophytis currently certifies a shelf life of the stability data of the Drug Product, Biophytis currently certifies a shelf life of the stability data of the Drug Product, Biophytis currently certifies a shelf life of the stability data of the Drug Product, Biophytis currently certifies a shelf life data of the stability data of the Drug Product, Biophytis currently certifies a shelf life data of the stability data of the Drug Product, Biophytis currently certifies a shelf life data of the stability data of the Drug Product, Biophytis currently certifies a shelf life data of the stability data of the Drug Product, Biophytis currently certifies a shelf life data of the stability data of the Drug Product, Biophytis currently certifies a shelf life data of the stability data of the Drug Product, Biophytis currently certifies a shelf life data of the stability data of the Drug Product, Biophytis currently certifies a shelf life data of the Stability data of t

6.2.4 PREPARATION

All treatment packages are delivered ready to be given directly to the participants. No further preparation is needed by the study Staff.

Study participants should be instructed to take 4 capsules per day everyday in a specific order: the first two **second** in the morning and the second two **second** in the evening.

If a dosing administration is skipped, study participants should start a **should** start a should not take the skipped capsules.

Important note: Date of each next visit should be calculated back on Day 0 visit (baseline) in order not exceeding the total duration of 26 weeks treatment (capped exposure)

6.2.5 SHIPMENT

Following GCP guidance on the situation of the public health emergencies, the core consensus guidelines for clinical trial management and the study DSMB recommendation, the safety of study patients and investigators is the priority during this COVID-19 outbreak. No on-site visit is allowed during the COVID-19 outbreak. Therefore, during this period and until further guidance, participants will receive their IPs at home with direct shipping/delivery from the study sites. The boxes are shipped to the participants' homes only after the site investigator/staff(s) have completed reviewing of all relevant safety study assessment resultsfrom the the scheduled calls. Shipment to the participant's homes are carried out based on a predefined and specific process to guarantee the proper shipment conditions that ensure study drug integrity. For intake of the drug, all participants have already been educated during previous on-site visits by the study staff and will already know the proper method and schedule for drug intake.

6.3 MEASURES TO MINIMIZE BIAS: RANDOMIZATION AND BLINDING

Randomization will be stratified by center and by gender. Randomization is performed online at the time of the inclusion visit for each study participant fulfilling all the inclusion and non-inclusion criteria, according to the appropriate ratio. The randomization procedure is embedded within the eCRF, which is based on the **appropriate state** by **a** 21CFR Part 11 compliant system.

Each treatment kit will show a pre-printed kit number affixed on the primary, secondary and tertiary containers. The kit number will be assigned via the eCRF after a patient qualifies and is randomized. Neither the Investigator, the staff or the Sponsor will be aware of the treatment that corresponds to the kit number. The assigned treatment cannot be retrieved from the system unless a specified **unblinding** procedure is engaged by the investigator. Unblinding can only occur when it is deemed necessary by the responsible physician of the investigation center in the context of a severe or serious adverse event.

The randomization list will be provided by **to** to the manufacturer and to the eCRF identified responsible person. The randomization list will not be available to the Sponsor staff, study participants, investigators, monitors or employees of the clinical site involved in the management of the study before unblinding of the data (after database lock), except in case of emergency.

The Clinical Research Organization (CRO) team from performing the data management and statistical activities will receive a copy of the randomization list after database lock.

A specific unblinding procedure will be made available in the eCRF for the investigator to perform emergency unblinding of a given patient for documented reasons. An unblinding procedure can only be engaged in an emergency situation where the Investigator considers it essential to know what treatment the subject was receiving. The monitor shall be notified promptly if unblinding is performed. It is recommended that the Investigator contacts the **section** medical monitor before unblinding, if possible. The investigator will document the date, time, and reason for the unblinding in the patient's medical records.

It is the investigator's responsibility to ensure that there is a procedure in place to allow access to the remote system in case of emergency. The investigator will inform the subject how to contact his/her backup in case of emergencies when he/she is unavailable.

Should the code be (intentionally or unintentionally) broken by the Investigator or by a clinical staff, whether the subject could remain in the study or not should be judged by the Investigator

according to the subject's best interest. The event will be immediately reported to the Sponsor and to and dealt with as a major protocol deviation.

The subject's clinical data will not be analyzed in the per protocol set.

6.4 STUDY INTERVENTION COMPLIANCE

During the COVID-19 outbreak, all participants will be asked to send back all used and unused boxes containing the investigational study drug. These returns are carried out based on the same predefined and specific process as the one applied for the shipment from site to participants home. Adherence to the protocol will be assessed by the Investigator staff by counting the full and empty blisters.

A participant study drug log will be completed (to be kept in the source documents) and recorded into the eCRF. An algorithm will automatically calculate the adherence based on visit dates.

6.5 CONCOMITANT THERAPY

For this protocol, a prescription medication is defined as a medication that can be prescribed only by a properly authorized/licensed clinician. Medications to be reported in the CRF are concomitant prescription medications, over-the-counter medications and supplements.

The following medications are not allowed during the study:

- 1. Anabolic drugs e.g. testosterone, growth hormone, etc. (replacement hormonal treatment for menopause is allowed if started at least 3 months before randomization without dose changing)
- 2. Anabolic supplements, e.g. branched-chain amino acids, anabolic treatments, or treatments containing 20E
- 3. Herbal treatments containing
- 4. Erythropoietin
- 5. Corticosteroid agents chronically administered per oral or parenteral route (except local administration route such as eye drops or dermatologic formulations; except emergency parenteral administration for acute conditions like asthma, allergic reactions, etc.)
- 6. Chemotherapy
- 7. Radiotherapy
- 8. Androgen suppressant treatments (e.g. finasteride); estrogen suppressant treatments (e.g. tamoxifen)

Should a participant need or report the use of these drugs during the study due to treatment for an AE, the physician will make the decision to withdraw or to keep the patient in the study according to the patient's best health interest.

6.5.1 RESCUE MEDICINE

There is no specific rescue medicine for BIO101. Standard medical measures should be taken in case of an accidental or deliberate overdose of BIO101.

7 STUDY INTERVENTION DISCONTINUATION AND PARTICIPANT DISCONTINUATION/WITHDRAWAL

7.1 DISCONTINUATION OF STUDY INTERVENTION

The Investigator should discontinue study intervention and specifically ensure that a participant stops taking the investigational drug if the bioanalytical results at Month 1 or Month 3 shows the following changes:

1. Confirmed 3-fold or greater elevations above the Upper Limits of Normal (ULN) of

These stopping rules for discontinuation are established based on

Discontinuation from investigational oral treatment does not mean discontinuation from the study, and remaining study procedures should be completed as indicated by the study protocol. If a clinically significant finding is identified (including, but not limited to, changes from baseline) after enrollment, the investigator or qualified designee will determine if any change in participant management is needed. Any new clinically relevant finding will be reported as an AE.

The data to be collected at the time of study intervention discontinuation will include the following:

- AE complete follow-up (if the treatment is stopped following an AE)
- Last investigational medication administration date and time

The physician can decide to re-introduce the investigational treatment if it was stopped because of a concomitant acute condition he/she considers unrelated to the treatment.

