- Study drugs will continue to be dispensed and provided to participants through direct shipping from study site to the participants' home after the site investigator/staff(s) have completed reviewing all relevant safety study assessment results from the calls.

- An updated strategy for the final analysis will be implemented, to account for the missing data on safety and efficacy which will have impact on the final analysis. The planned interim analysis is postponed to a time after the restrictions are lifted. Both updated are described in a new version of the Statistical analysis Plan.

- As certain assessments/tests cannot be conducted per protocol, the investigator/site staff(s) should evaluate the overall risk/benefit, and contact the sponsor related staff(s) promptly should there be any safety concerns in order to reach agreement on how to proceed. This may require *ad hoc* safety assessments (e.g. safety blood draw, communication with participant's HCP). Additional checks should be performed as soon as the conditions allow it or at the end of the outbreak restrictions based on the national/federal, state and local governance.

- An extension for treatment of 3 additional months is proposed for those participants missing the efficacy assessments at Month 6 visit/End-of-intervention. This would allow for the addition of data on safety and efficacy for the final analysis.

Study Duration: 33-35 months

Participant Duration:

Up to 39 weeks + screening (1-8 weeks) + follow-up at 6 weeks post study conclusion

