7.2 PARTICIPANT DISCONTINUATION/WITHDRAWAL FROM THE STUDY

Participants are free to withdraw from participating in the study at any time upon request.

An investigator may discontinue or withdraw a participant from the study for the following reasons:

- Pregnancy: however, in principle, only menopaused women are eligible in this protocol
- Significant study intervention non-compliance
- If any clinical AE, laboratory abnormality, or other medical condition or situation occurs such that continued participation in the study would not be in the best interest of the participant
- Disease progression which requires discontinuation of the study intervention
- If the participant meets an exclusion criterion (either newly developed or not previously recognized) that precludes further study participation
- Participant unable to receive oral treatment for more than 4 weeks

The list above is provided as considerations to guide the investigators and the decision to discontinue or withdraw a participant is up to the investigator's discretion. A study participant is allowed to continue in the study, given his/her own choice, even if he/she needs to stop the study drug intervention.

The reason for participant discontinuation or withdrawal from the study will be recorded in the eCRF. Based on the number of study participants enrolled in each center, study participants who signed the informed consent form and are randomized but do not receive the study intervention may be replaced. Study participants who signed the informed consent form were randomized and received the study intervention, but subsequently withdrew, or are withdrawn or discontinued from the study, will not be replaced.

In any case, each subject needs to be randomized via the eCRF procedure, and already assigned TUs cannot be manually assigned to a new participant.

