- **Biological specimen collection and laboratory evaluations:** Blood samples will be collected by venepuncture or via indwelling cannula at screening, M1, M3 and at M6 visits for biochemistry and analyses. In case of previous abnormalities or new symptoms, a blood sample can be collected at M5
 - a. **Hematology**: hemoglobin, HbA1c, hematocrit, red blood cell (RBC) count, white blood cell (WBC) count with differential, platelet count, mean corpuscular haemoglobin, mean corpuscular haemoglobin concentration, mean corpuscular volume
 - b. Biochemistry: sodium, potassium, chloride, bicarbonate, urea, uric acid creatinine, albumin, glucose, cholesterol (total cholesterol, LDL, HDL fractions), triglycerides, aspartate aminotransferase (AST), alanine aminotransferase (ALT), alkaline phosphatase, bone-specific alkaline phosphatase, lipase, amylase, gamma glutamyl aminotransferase, bilirubin (total, indirect, direct), creatine phosphokinase and mb-creatine phosphokinase, lactate dehydrogenase, total protein, and GFR estimation based on Cockroft & Gault calculation
 - c. **Coagulation**: activated partial thromboplastin time, prothrombin time, and international normalized ratio.
 - d. **Urine analysis**: A midstream urine sample will be collected for urinalysis by dipstick for glucose, protein, and occult blood

All study analyses will be performed by a centralized laboratory. The Investigator must review the laboratory report, document this review, and record any changes occurred during the study. Laboratory values outside the normal ranges will be flagged and their clinical relevance will be assessed by the Investigator. **See also Exclusion criteria based on lab results and stopping rules in Section 5.3** Exclusion criteria and temporary exclusion criteria and **Section 7.1** discontinuation of study intervention, respectively.

- **Counseling procedures, including any dietary or activity considerations**: see section 5.4 Lifestyle considerations
- Assessment of study intervention adherence: see Study Intervention Compliance, section 6.4
- Administration of the PROs: see Efficacy Assessments, Section 8.1

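### The visible 3 x ULN stopping rule in protocol 7.1 applies only to Month 1 and Month 3 results, so Month 5, ad hoc and catch-up results on treatment have no visible numeric threshold

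*Protocol*

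**What the plan says.** Section 7.1 of the protocol sets a laboratory stopping rule. The investigator should make sure that a participant "stops taking the investigational drug if the bioanalytical results at Month 1 or Month 3 shows the following changes". The one visible item is a confirmed elevation to at least three times the ULN. The analytes, the stated basis and possibly further items are blacked out. The limit to two months is in the unredacted lead-in.

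Other places bear on which blood results exist and what is done with them:

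- Section 8.2 gives the sampling plan: "Blood samples will be collected by venepuncture or via indwelling cannula at screening, M1, M3 and at M6 visits". It adds a conditional sample: "In case of previous abnormalities or new symptoms, a blood sample can be collected at M5". It refers the reader to section 7.1 for stopping rules, and has the investigator review each report and assess out-of-range values.
- The Schedule of Activities (1.3) in version 1.2.11 replaces the M1, M3 and M6 visits with telephone calls during the outbreak. It lists haematology and biochemistry only at screening and at week 39 or end of intervention.
- Section 4.1 caps exposure at 39 weeks. The synopsis offers the three extra months to participants who miss the Month 6 efficacy assessments.
- The synopsis allows ad hoc safety blood draws and says: "Additional checks should be performed as soon as the conditions allow it or at the end of the outbreak restrictions". If there is a safety concern, the site must contact the sponsor promptly and agree how to proceed.
- For a clinically significant finding, 7.1 says "the investigator or qualified designee will determine if any change in participant management is needed". Section 7.2 names a laboratory abnormality as a ground for withdrawal but adds: "The list above is provided as considerations to guide the investigators".
- Section 10.1.6 has the DSMB review bioanalytical data every three months.

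**The concern.** The month limit suited the 26-week plan. M1 and M3 were then the only scheduled on-treatment bloods before the M6 end visit, so every scheduled result that could still lead to a stop was covered. Only the conditional Month 5 sample was left out.

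Under version 1.2.11, a participant whose M1 and M3 visits become calls may have no blood result at a time the rule names. The results that can still change dosing come mainly from the Month 5 sample, ad hoc draws and catch-up checks made while still on drug. Two of these are prompted by a reason to look: the Month 5 sample follows earlier abnormalities or new symptoms, and ad hoc draws follow a safety concern. As the visible text reads, a confirmed three-fold elevation at Month 3 calls for a stop. The same confirmed value at Month 5 is a matter for judgement, which may differ between sites, and under the extension more dosing may lie ahead.

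**Working it through.** The plan gives no figure on this point to reproduce. The check compares texts and adds a short calculation of dosing time.

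**Step 1. Which results does the visible rule cover?**

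| Blood result | Source | Can it still prompt a stop? | Named in the visible 7.1 rule? |
|---|---|---|---|
| M1, M3 | 8.2; calls under 1.3 | Yes, if drawn | Yes |
| Conditional Month 5 sample | 8.2 | Yes | No |
| Ad hoc safety draw | Synopsis | Yes, if on drug | Only if it falls at Month 1 or 3 |
| Catch-up check | Synopsis | Only if made on drug | Only if it falls at Month 1 or 3 |
| M6, 26-week plan | 8.2 | No, end of treatment | No |
| Week 39 or end of intervention | 1.3 | No, end of treatment | No |

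**Step 2. Does other visible text supply a threshold?** The second provision in 7.1, the list in 7.2 and the review of flagged values in 8.2 all leave action to the investigator. The sponsor contact in the synopsis is a process without a stated value. DSMB review is periodic and is not an individual trigger. Section 6.2.5 holds home shipment until safety results from the calls have been reviewed, again with no laboratory limit. None gives a number.

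**Step 3. How much dosing can lie ahead of a Month 5 result?**

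Inputs: Month 5 contact at week 21, window plus or minus 1 week (1.3); planned treatment 26 weeks; exposure cap 39 weeks (4.1).

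Formula: weeks ahead = end of dosing minus week of result.

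| Week of result | 26-week plan | 39-week cap |
|---|---|---|
| 20 | 26 - 20 = 6 | 39 - 20 = 19 |
| 21 | 26 - 21 = 5 | 39 - 21 = 18 |
| 22 | 26 - 22 = 4 | 39 - 22 = 17 |

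These are upper limits for one participant with a confirmed elevation who takes the full extension.

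**Step 4. How much of treatment falls after the last named time point?** Month 3 is week 12 (1.3). Under the 26-week plan the share is (26 - 12)/26 = 14/26 = 54%. Under the 39-week cap it is (39 - 12)/39 = 27/39 = 69%. This describes time only. It is not a share of results or of participants.

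**The case against.** The strongest reply is that later elevations are not ignored. Investigators must review every report, a laboratory abnormality is a listed ground for withdrawal, and outbreak safety concerns go promptly to the sponsor for agreement. The rule itself says only that the investigator should stop the drug. All of this stands. A reader might infer that a participant with a late elevation must stay on drug, and the documents do not support that: what is missing is a visible threshold, not the power to stop.

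Other stronger readings also go too far:

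- *That version 1.2.11 created the gap.* The Month 5 sample was already outside the wording. The amendment lengthened the dosing that can follow it and removed many of the covered results.
- *That the month limit is arbitrary.* The sentence giving the basis for the rules is redacted, and so may be further rules. Missing reasons cannot be counted against the plan.
- *That no one has M1 or M3 bloods, or that every unscheduled draw is uncovered.* Section 8.2 still lists those draws, the calls are tied to the outbreak, and an unscheduled draw may fall at Month 1 or 3. A catch-up check may also coincide with the end visit, when there is nothing left to stop.
- *That a week-26 result leaves 13 weeks (39 - 26) against none.* The extension is for participants who missed the Month 6 assessments, and 1.3 schedules no bloods at the Month 6 call. The figure needs an unscheduled draw at that time.

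Two further replies have some force. Confirming an M1 or M3 elevation would normally take a repeat sample after that visit, so the rule is probably not meant with complete literalness. But that helps only when the first elevation was at Month 1 or 3. Also, 8.2 assigns study analyses to a central laboratory, and the text does not say which laboratory or reference range would serve an ad hoc draw. That is a practical question for the wider rule, but no reason to leave such results without a threshold.

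**Conclusion.** The point holds as a limited gap in the visible wording. For a Month 5, ad hoc or on-treatment catch-up result that does not fall at Month 1 or 3, the visible protocol gives no numeric stopping threshold. It relies on investigator judgement and, for outbreak safety concerns, on agreement with the sponsor. The dosing that a stop at Month 5 could prevent rises from about 5 weeks to as much as about 18 in a participant who takes the full extension.

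This rests on two assumptions. First, no redacted item already covers other time points. Second, the 39-week cap in 4.1 governs, although 6.1.2, 6.2.4 and the note under the schedule in 1.3 still state 26 weeks. With the analytes hidden, the clinical weight cannot be judged, and the number of participants affected cannot be derived. The change is worth considering as a cheap improvement. Confidence is medium.

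**What to change.** In section 7.1, replace the reference to Month 1 or Month 3 with: *at any on-treatment assessment, scheduled or unscheduled, up to the end of intervention*. Keep the requirement that the elevation be confirmed, which guards against stopping on a single spurious value.

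The change is one phrase and adds no blood draw. It does not replace M1 or M3 results lost to telephone visits; it only fixes how the results that do exist are acted on. The cost is possibly a few more treatment stops. Under 7.1 those participants remain in the study for the remaining procedures.
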